### 3.0 Intervention to be studied

PE will be delivered to all participants based on Foa’s therapy manual (Foa et al., 2019). Therapy sessions will be delivered once or twice per week up to 10 weeks. All participants will wear the IB-PE system, affording maximum data collection during IVEs and thorough evaluation of the new system. Using a 3 to 1 randomization scheme (3 guided: 1 record only), the participants will be randomly assigned to either IB-PE (guided) or to IB-PE (record only). A description and images that describe the system are provided below:

The Zeriscope system includes a customized (1) patient interface, (2) clinician interface, and (3) cloud-based system specifically designed for IB-PE (Figure 1). The patient interface consists of (a) wearables that enable continuous collection of quantitative (e.g., heart rate) and qualitative data (e.g., video) with as little burden as possible to the patient, and (b) software application on a mobile phone. All participants will be provided a mobile phone to use during the study. The prototype tested in the prior feasibility pilot study will be enhanced to include: (a) local (phone) session storage when no cellular or WiFi service is available to prevent loss of connection, (b) keypad for self-report of SUDS, (c) application login and authentication, and (d) intuitive user control and notification features. The wearables will be comfortable and designed to be

Figure 2. Clinician Dashboard. (A) dashboard controls, (B) live video feed from patient, (C) geolocation, and (D) real-time streaming of heart rate and skin conductance.

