## **6.0 Number of Subjects**

40 participants will be enrolled.

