As shown in **Figure 3**, 10 sessions of PE will be delivered, with the possibility for participants to complete two sessions per week. Prior to using the IB-PE system, participants will use the system to develop an 'in-office' baseline that will be used for reference throughout the IVEs. Another 'in-office' baseline will be recorded at final session to assess physiological and subjective changes that have occurred throughout the course of the treatment. All participants will wear the IB-PE system, affording maximum data collection during IVEs and thorough evaluation of the new system. The in vivo exercises will be guided by either the Study Therapist or a clinical support team member. This role will be referred to as the 'IVE Coach.' The participants will be randomly assigned to either IB-PE (guided) or to IB-PE (record only) based on a 3 to 1 randomization scheme (3 guided: 1 record only). In the guided group, the IVE Coach will lead the participant in the in vivo exercises. The IVE Coach will use actionable data during IVEs (e.g., HR, GSR) to modify the assignments in real time. The IVE Coach will virtually accompany patients to at least three IVEs. After that the IVE Coach will start out the session by guiding the participant for the first several minutes, then will leave the session once the participant demonstrates competency in finishing the exercise on his or her own. The IVE Coach will be in close communication with the rest of the clinical support team regarding the participant's IVE completion. Study Therapists will receive a system notification each time a patient completes an IVE, along with a summary report from that assignment (e.g., total time,  $\bar{x}$  and peak GSR). These data may be used to objectively monitor treatment progress and discussed with the patient in the office (e.g., to highlight habituation within or between IVEs) (Rauch et al., 2018). In the record-only group, passive data collection will be utilized to collect and store biometric and behavioral data for future offline analyses to investigate predictors of outcome. Wifi availability will be considered in the selection of the therapist-guided locations for IVEs. In the rare event that wifi signal is not present during a therapist-guided IVE, the participant and IVE Coach would work together to find an alternate solution (complete the IVE without wifi, and/or complete an additional therapist-guided IVE at another time and location, and/or reevaluate the in vivo hierarchy and make modifications to include locations with wifi). If equipment malfunctions at any point throughout the study, a replacement system will be provided to the participant. Zeriscope will be notified of equipment malfunctions.

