**General Statistical Analyses.** All analyses will be performed on the intent-to-treat sample consisting of all randomized subjects. Baseline clinical and demographic characteristics will be collected and t-tests, chi-square tests, or their non-parametric equivalents will test for group differences, as appropriate, in SAS v9.4 (SAS Institute, Cary, NC, USA). Baseline characteristics that are associated with the primary outcome measures will be included as covariates in subsequent analyses. For all analyses, alpha will be set at 0.05. Urn randomization will be stratified by PTSD severity (CAP-5 total score at baseline). Based on our sample size and assuming 20% attrition (N=32), we have 80% power to detect a large effect (Cohen's  $d = 1.02$ ) for treatment outcome at a probability level of 0.05 for a two-tailed test (Cohen, 1988).

Hypothesis 1: IB-PE will be feasible and acceptable, as evidenced by at least 80% of participants (a) being able to turn on/off the equipment in  $\leq 5$  minutes; (b) reporting positive perceptions toward IB-PE via self-report assessments (Sekhon, Cartwright, & Francis, 2017). Hypothesis 2: Participants in the IB-PE guided group will evidence significantly greater pre- to post-treatment reductions in PTSD severity as compared to the record-only group. To test this hypothesis, independent generalized linear mixed effects models will be used to examine PCL-5 and CAPS-5 scores at final session by group. Models will be adjusted, respectively, for baseline PCL-5 and CAPS-5. Group will be entered as the predictor variable. Hypothesis 3: Higher levels of physiological and subjective engagement will predict greater treatment response. To test this hypothesis, mean HR, GSR, and SUDS responses during IVEs will be calculated according to previously published methods (Norholm et al., 2016; Rauch et al., 2018; Rothbaum et al., 2014) and multilevel modeling (MLM) will be used to analyze these variables as predictors of CAPS-5 at final session within and between treatment groups.

Exploratory analyses will examine group differences in the number of sessions required to attain significant symptom improvement on the PCL-5 from baseline (Rothbaum et al., 2014) and durability of effects at 1-month follow up. Data from both groups will be harnessed to explore the development of patient-specific algorithms predicting optimal engagement during IVE.

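### The 80% power stated for d = 1.02 at N=32 leaves out the 3:1 allocation; at 24:8 an unadjusted two-sided t-test has about 68% power, and reaches 80% only at d = 1.18

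*Combined protocol and SAP*

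**What the plan says.** Section 6.0 sets the sample size: "40 participants will be enrolled". The allocation is given twice, in section 3.0 ("Using a 3 to 1 randomization scheme (3 guided: 1 record only") and in section 10.0 ("based on a 3 to 1 randomization scheme (3 guided: 1 record only").

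The power statement is in General Statistical Analyses, section 11.0: "Based on our sample size and assuming 20% attrition (N=32), we have 80% power to detect a large effect". The effect is Cohen's d = 1.02, two-tailed, at 0.05. The statement gives no arm sizes, allocation ratio, test or baseline correlation.

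The same section contains four other relevant provisions:
- Analysis set: "All analyses will be performed on the intent-to-treat sample consisting of all randomized subjects".
- Randomization: "Urn randomization will be stratified by PTSD severity".
- Models for Hypothesis 2: "Models will be adjusted, respectively, for baseline PCL-5 and CAPS-5".
- Further covariates: "Baseline characteristics that are associated with the primary outcome measures will be included as covariates in subsequent analyses".

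Section 13.0 (Data Management and Analysis) describes the study as powered for efficacy on the primary outcomes, and also plans effect sizes with 95% confidence intervals. Section 1.0 and the protocol summary in section 13.0 call the efficacy aim preliminary.

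**The concern.** For a fixed total, a comparison of two means is most precise with equal arms and loses precision as the arms become unequal. A power figure for a 3:1 trial therefore has to use the 3:1 arm sizes. The figure here appears not to, since it agrees almost exactly with an equal split of 32.

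Hypothesis 2 is a significance test of guided against record-only. A reader of section 11.0 would take the chance of missing a true effect of d = 1.02 to be 20%. Without a covariate gain it is about 32% (100% minus 68%). With about eight record-only completers, a non-significant result could be over-read as evidence that guidance adds nothing.

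**Working it through.** **Inputs from the plan.** 40 participants (section 6.0); 3:1 allocation (sections 3.0 and 10.0); 20% attrition, N=32, d = 1.02, two-sided 0.05 and 80% power (section 11.0).

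**Assumptions not in the plan.** The 40 split exactly 30:10, attrition is equal by arm, and any baseline-to-final correlation r.

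**Arm sizes.** 40 × 0.8 = 32. At 3:1, 30 × 0.8 = 24 guided and 10 × 0.8 = 8 record-only.

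**Formula.** Two-sample t-test, noncentral t: ncp = d × √(n1·n2/(n1+n2)), df = n1 + n2 − 2. With df = 30 the two-sided critical value is 2.042.

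**Step 1: reproduce the plan's figure with equal arms.** 16·16/32 = 8, so ncp = 1.02 × √8 = 2.885. Power is 79.7%, and 80% is reached at d = 1.024. This matches the stated 80% at d = 1.02.

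**Step 2: use the trial's allocation.** 24·8/32 = 6, so ncp = 1.02 × √6 = 2.498. Power is 0.6765, about 68%. The d for 80% power is 1.182. As a check, the detectable d scales with √(8/6) = 1.155, and 1.024 × 1.155 = 1.18.

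**Step 3: vary the split.** Urn randomization does not fix the arm totals, and attrition may differ by arm. Unadjusted, two-sided:

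| Guided : record-only | Power at d = 1.02 | d for 80% power |
|---|---|---|
| 16:16 | 79.7% | 1.02 |
| 20:12 | 77.1% | 1.06 |
| 21:11 | 75.6% | 1.08 |
| 22:10 | 73.5% | 1.10 |
| 23:9 | 70.9% | 1.14 |
| 24:8 | 68% | 1.18 |
| 25:7 | 63.6% | 1.24 |
| 26:6 | 58.7% | 1.31 |
| 30:10 (all 40 analysed) | 77.7% | 1.05 |

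None of the unequal splits of 32 reaches 80%. Analysing all 40 without loss does not reach it either.

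**Step 4: allow for baseline adjustment at 24:8.** One covariate, df = 29, with d on the unadjusted SD scale. The upper end assumes no chance baseline imbalance and divides ncp by √(1 − r²). For example, at r = 0.5, ncp = 2.498/√0.75 = 2.885. The lower end averages power over chance imbalance under unrestricted randomization.

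| Assumed r | Lower end | Upper end |
|---|---|---|
| 0.3 | 70.2% | 71.6% |
| 0.4 | 73.6% | 75.0% |
| 0.5 | 78.3% | 79.6% |
| 0.6 | 84.3% | 85.5% |

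Power reaches 80% at r = 0.507 (upper end; r² = 0.257) or r = 0.531 (lower end; r² = 0.282). An ANCOVA simulation of 200,000 trials agrees with the lower end: 69.9%, 73.4%, 78.2% and 84.4% at the four values of r, and 79.9% at r = 0.53. Stratifying on CAPS-5 would move the CAPS-5 analysis towards the upper end. Each added covariate raises the explained variance needed: at the lower end, 0.309, 0.336 and 0.363 with two, three and four covariates.

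**The case against.** The strongest objection is that an unadjusted t-test is not the planned analysis. The Hypothesis 2 models adjust for the baseline score, and other prognostic covariates may be added. If adjustment explains roughly 26–28% of outcome variance, power at 24:8 is 80%. The documents therefore cannot show that the planned analysis has less than 80% power. This point stands. But the plan gives no correlation and claims no covariate gain, and at r of 0.3 to 0.4 power is still only about 70–75%. If d = 1.02 was meant on the adjusted scale, adjustment adds nothing further.

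A second objection is that equal arms are an inference. They are: the plan does not say how the figure was obtained. The finding does not depend on that, only on whether the figure follows from the stated N, alpha and allocation. An alternative route, all 40 at 30:10 by normal approximation, gives 79.8%, but it ignores the attrition that the sentence itself builds in. The intent-to-treat provision fails for the same reason, because the power is explicitly based on 32.

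Third, 24:8 rests on an exact 30:10 split and equal attrition. That is so, and the point value moves with the split, but the direction does not.

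Finally, this is a small trial with a preliminary efficacy aim and planned confidence intervals. That limits the consequence but does not make the stated figure correct, and section 13.0 still describes the study as powered for efficacy.

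**Conclusion.** The concern holds. With N=32 and 3:1 allocation, the stated 80% power for d = 1.02 cannot be obtained without a covariate gain that the plan does not state. At 24:8, unadjusted and two-sided at 0.05, power is about 68%, roughly 12 percentage points lower (80 − 68), and the detectable effect at 80% power is d = 1.18 rather than 1.02. The exact values assume a 30:10 split and equal attrition; the shortfall remains at every other unequal split of 32 examined. With adjustment, 80% would need a baseline-to-final correlation of about 0.51 to 0.53 or more, which the documents neither give nor rule out. This is a correction to a stated figure and should be made. It does not call the design or the planned analysis into question.

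**What to change.** Replace the power sentence in section 11.0 with, for example:

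> With 3:1 allocation and 20% attrition, equal by arm (24 guided, 8 record-only), an unadjusted two-sided t-test at 0.05 has 80% power for d = 1.18 and 68% power for d = 1.02.

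If the baseline adjustment is to be relied on, add the assumed correlation with its justification, and label the result approximate:

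> Adjusted for the baseline score, power for d = 1.02 is approximately 70–72%, 74–75%, 78–80% or 84–86% if the baseline-to-final correlation is 0.3, 0.4, 0.5 or 0.6.

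One justified value is enough; the full list is not required. Optionally, bring the description of the study as powered for efficacy in section 13.0 into line with the preliminary aim stated elsewhere.

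The cost is wording only: no added participants, visits or analyses. The one drawback is a less favourable stated figure, unless a correlation of about 0.5 or more can be stated and justified.

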## 1.0 Objectives / Specific Aims

Posttraumatic stress disorder (PTSD) is a debilitating mental health condition that increases suicide risk and affects up to 20% of military veterans and 8% of the general population. Prolonged Exposure (PE) is a highly efficacious, evidence-based, cognitive-behavioral therapy for PTSD. However, dropout rates are high (25-30%) and an estimated one-third of patients who complete PE remain symptomatic. The primary objective of this study is to test a technology-based system that will (1) enable clinicians and clinical support staff to virtually accompany patients during in vivo exposures (IVEs) exercises to enhance engagement and successful completion of the exercises, and (2) provide clinicians and clinical support staff with real-time streaming of physiological biomarkers of affective engagement--galvanic skin response (GSR) and heart rate (HR)--and subjective units of distress (SUDS). This *actionable data* will be used in real-time by clinicians to modify the exercises and avoid under- and over-engagement, thereby minimizing inefficiencies and maximizing therapeutic value of IVEs. Secondary objectives are to use *passive data* collection to characterize IVEs, identify predictors of change, and inform next steps. To accomplish this, Zeriscope, a local small business with experience developing cutting-edge mobile technology platforms for health care, has partnered with clinical researchers at the Medical University of South Carolina (MUSC) to (1) develop a technology-based system to use intelligent biometrics (IB) to optimize PE ("IB-PE"), and (2) compare the guided IVE intervention to a passive data record-only version which will collect and store biometric and behavioral data for offline analyses. The following Specific Aim is proposed:

**Specific Aim:** **Conduct a 10-session randomized clinical trial (N=40 treatment-seeking veterans/civilians with current PTSD) to evaluate the acceptability and preliminary efficacy of IB-PE and investigate predictors of outcome.** Milestones: (1a) Evaluate ability of IB-PE (guided vs. record only) in reducing PTSD severity from baseline to session 10; and (2b) Use GSR, HR and SUDS to characterize IVEs and identify how each of these indicators predicts treatment response.

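### The power statement plans on 20% attrition without giving a reason, below the protocol's own 25-30% PE dropout range; power should be shown over 20-30% attrition at the 3:1 allocation

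*Combined protocol and SAP*

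**What the plan says.** Section 6.0 sets the sample size: "40 participants will be enrolled". Section 11.0 (General Statistical Analyses) makes the only power claim: "Based on our sample size and assuming 20% attrition (N=32), we have 80% power to detect a large effect", namely d = 1.02, "for treatment outcome at a probability level of 0.05 for a two-tailed test". That paragraph does not say where the 20% comes from, which test was used, or what allocation was assumed.

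Section 1.0 gives the only dropout figure in the document, as part of the case for the trial: "However, dropout rates are high (25-30%) and an estimated one-third of patients who complete PE remain symptomatic".

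Other parts bear on the point:

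- Section 3.0 says that every participant receives PE and that randomization is 3 guided to 1 record only. Section 10.0 repeats the ratio.
- Section 11.0 analyses all randomized subjects and models PCL-5 and CAPS-5 at the final session, adjusted for baseline. It names no method for missing outcomes.
- Table 1 schedules the CAPS-5 at baseline, after treatment and at one month only. The PCL-5 is also collected during sessions 1-9.
- Section 13.0 (Data Management and Analysis) relies on the power claim when it describes the study as powered for efficacy on the primary outcomes.

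**The concern.** The planned attrition is 5 to 10 percentage points better than the range the protocol itself reports for the therapy given in both arms, and no reason is offered. The power paragraph turns attrition directly into lost sample size (40 to 32), so a higher rate lowers the analysable N, lowers the power and raises the detectable effect. A reader of a null result would then credit the trial with more ability to detect a difference than its own background evidence supports.

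**Working it through.** **Inputs.** Enrolled 40 (section 6.0). Attrition 20%, d = 1.02, two-sided 0.05 and stated power 80% (section 11.0). PE dropout 25-30% (section 1.0). Allocation 3:1 (sections 3.0 and 10.0).

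**Step 1: analysable N.**

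- 20%: 40 × 0.80 = 32
- 25%: 40 × 0.75 = 30
- 30%: 40 × 0.70 = 28

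The last two assume that each dropout loses the final score.

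**Step 2: formula.** Two-sample t-test, two-sided 0.05, noncentral t distribution with df = n1 + n2 − 2 and noncentrality δ = d × √(n1·n2/(n1 + n2)).

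**Step 3: reproduce the plan's figure.** With 16 v 16, δ = 1.02 × √8 = 2.885 on 30 df. Power is 79.7%, and the effect detectable with 80% power is 1.024. The stated 80% and d = 1.02 are therefore reproduced, but only with equal arms. With the protocol's 3:1 split, 24 v 8, δ = 1.02 × √6 = 2.498 and power is 67.7%.

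**Step 4: change attrition alone, on the equal-arm basis.** This isolates the cost of the attrition input.

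| Attrition | Arms | δ | Power at d = 1.02 | d for 80% power |
|---|---|---|---|---|
| 20% | 16 v 16 | 2.885 | 79.7% | 1.02 |
| 25% | 15 v 15 | 2.793 | 76.9% | 1.06 |
| 30% | 14 v 14 | 2.699 | 73.8% | 1.10 |

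The loss is 79.7 − 76.9 = 2.8 points at 25% and 79.7 − 73.8 = 5.9 points at 30%.

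**Step 5: the same at 3:1, with equal attrition rates in the two arms.**

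| Attrition | Arms | δ | Power at d = 1.02 | d for 80% power |
|---|---|---|---|---|
| 20% | 24 v 8 | 2.498 | 67.7% | 1.18 |
| 25% | 22.5 v 7.5 | 2.419 | 64.6% | 1.22 |
| 30% | 21 v 7 | 2.337 | 61.4% | 1.27 |

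At 25% the exact 3:1 split is not in whole patients; 22 v 8 gives 66.5% and 23 v 7 gives 62.6%. The attrition loss is again about 3 to 6 points (67.7 − 64.6 = 3.1; 67.7 − 61.4 = 6.3). Allocation costs more: 79.7 − 67.7 = 12.0 points at the plan's own 20%.

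**Step 6: baseline adjustment.** The planned model adjusts for the baseline score, but the document gives no baseline-outcome correlation. If d = 1.02 is on the unadjusted SD, a correlation r raises the effective effect to 1.02/√(1 − r²). At 3:1, and ignoring the one degree of freedom spent on the covariate:

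| Assumed r | 20% | 25% | 30% |
|---|---|---|---|
| 0 | 67.7% | 64.6% | 61.4% |
| 0.3 | 71.7% | 68.7% | 65.5% |
| 0.5 | 79.7% | 76.9% | 73.8% |

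**The case against.** The strongest reply is that nothing has been miscalculated. 40 × 0.80 is 32, and 79.7% rounds to 80% on equal arms. The 25-30% describes PE in general and is used to motivate the trial; it does not forecast this trial's missing data. That stands. A reader might infer that the plan contradicts its own attrition figure, but the plan's attrition figure is 20%.

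A reader might also infer that a patient who leaves therapy necessarily loses the outcome. The document does not say so. The analysis covers all randomized subjects, there is a post-treatment CAPS-5, and nothing rules out assessing people who have stopped therapy. Equally, nothing provides for it: no off-treatment assessment and no missing-data method is named, and the CAPS-5 has no score between baseline and post-treatment to inform a missing final value. The question is open, so the 28 to 30 is conditional.

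There is also some support for a rate below 25%. Section 2.0 hopes that the system will reduce attrition. Section 10.0 expects telehealth to help retention, pays $30 for each of 10 visits and $50 at follow-up, and allows two sessions a week. Telehealth, payment and flexible scheduling are open to both arms; only live guidance is not. None of these carries a retention figure, and the power paragraph cites none of them. They make 20% arguable but do not establish it.

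Finally, the effect is modest: 2 to 4 patients, 3 to 6 points, and a detectable effect that stays large. The trial aims at preliminary efficacy and promises confidence intervals, and allocation matters more. All of this is fair. It limits the weight of the point and means that power should be restated once, with both inputs handled together.

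**Conclusion.** The point holds as an unjustified, optimistic planning input, not as an arithmetic error. If PE dropout of 25-30% applied here and led to missing final scores, N would be 28-30 rather than 32 and power about 3 to 6 points lower, on either allocation basis.

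It is tempting to conclude that true power is 74-77%, or that the detectable effect is 1.06-1.10. The document does not support those as figures for this trial, because they assume equal arms and the trial randomizes 3:1. At 3:1, an unadjusted t-test has about 68%, 65% and 61% power at d = 1.02 for 20%, 25% and 30% attrition.

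These results assume similar attrition in the two arms and no gain from baseline adjustment. A useful baseline correlation would raise them, but its size is not given.

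**What to change.** In section 11.0 (General Statistical Analyses), do one of two things: state the reason for 20%, or replace the single figure with a 20-30% range (N = 28-32) that refers to the dropout range in section 1.0. In either case, restate power and detectable effect at 3:1. Suitable wording would be:

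> With 3:1 allocation and 20%, 25% or 30% attrition (N = 32, 30 or 28), an unadjusted two-sided t-test at 0.05 has about 68%, 65% or 61% power at d = 1.02. The effect detectable with 80% power is d of about 1.18, 1.22 or 1.27.

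Any gain from baseline adjustment should be added as a labelled assumption that states the correlation used. The equal-arm values (1.06-1.10; 74-77%) should not be inserted.

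The cost is a sentence or two and a less favourable stated figure. Enrolment, procedures and analysis do not change, and no extra patients are needed.

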**Assessments.** The instruments to be used were selected because many are standardized, have good psychometric properties, are widely used, and have been used by our research group. The primary outcome measures are described in this section. Information regarding additional measures can be found in Table 1.

Primary clinical outcomes include: the CAPS-5 for clinician-rated and PCL-5 for self-reported PTSD symptoms. The CAPS-5 is a 30-item structured diagnostic interview and gold standard for assessing PTSD (Weathers, Blake, et al., 2013). Independent evaluators blind to treatment condition will conduct the CAPS-5 at baseline, end of treatment, and follow up. The PCL-5 is a 20-item self-report measure that assesses PTSD severity each week and has excellent psychometric characteristics (Weathers, Litz, et al., 2013). IVE assessments include: psychophysiological reactivity (HR and GSR), which will be measured passively and continuously during IVEs using the patient worn data acquisition system (Zeriscope Inc.). Consistent with imaginal exposures, Subjective Units of Distress (SUDS; 0=no anxiety to 100=extreme anxiety) will be collected at 5-minute intervals during IVEs. A tone will signal patients to enter their SUDS using the device. Self-report questionnaires employed in our pilot feasibility study and other studies will assess comfort, acceptability, willingness to use, utility, and client satisfaction (Attikisson & Greenfield, 2004; Rizzo et al., 2010).

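### The PCL-5 primary model does not prespecify baseline CAPS-5, the stratification variable, and leaves its entry to an association screen with no stated criterion

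*Combined protocol and SAP*

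**What the plan says.** Both scales are primary. Section 10.0 (Assessments) states "Primary clinical outcomes include: the CAPS-5 for clinician-rated and PCL-5 for self-reported PTSD symptoms".

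Section 11.0 (General Statistical Analyses) then has three sentences that bear on the covariates:

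- Allocation: "Urn randomization will be stratified by PTSD severity (CAP-5 total score at baseline". No cut-points or urn parameters are given.
- General rule: "Baseline characteristics that are associated with the primary outcome measures will be included as covariates in subsequent analyses". No test, threshold or candidate list is given, and the rule does not say whether association is judged separately for each outcome.
- Hypothesis 2 models: "Models will be adjusted, respectively, for baseline PCL-5 and CAPS-5". The word *respectively* pairs baseline PCL-5 with the PCL-5 model and baseline CAPS-5 with the CAPS-5 model.

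No reason is given for treating the stratification variable differently in the two models. Table 1 schedules the CAPS-5 at baseline, so the value is available for everyone.

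**The concern.** An analysis should reflect the way participants were allocated. Balancing the arms on a prognostic variable limits that variable's contribution to the error of the treatment estimate. If the model then omits it, whatever outcome variance it explains beyond the other covariates stays in the residual, and the model-based standard error can come out somewhat larger than it need be.

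The second issue is prespecification. As written, the covariate set of one primary model is unknown until outcomes have been examined. With about 32 completers, entry of baseline CAPS-5 would turn on one noisy observed association, judged by an unstated standard. A variable that belongs in the model because of the design should not have to qualify on the data. The record-only arm would have about 8 completers, so an avoidable analyst choice on a primary outcome is worth closing.

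**Working it through.** **Inputs from the documents.** 40 enrolled (section 6.0); "Using a 3 to 1 randomization scheme (3 guided: 1 record only" (section 3.0); "Based on our sample size and assuming 20% attrition (N=32), we have 80% power to detect a large effect", with d = 1.02, alpha 0.05, two-tailed (section 11.0). At 3:1, 32 completers are 24 guided and 8 record only.

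**The plan's own figure.** A two-sample t-test with d = 1.02 has 79.7% power at 16/16, which matches the stated 80%. At 24/8 it has 67.7%. That mismatch is a separate matter. It is noted here only because the comparison below uses 24/8 and covariate adjustment, so its power figures do not start from 80%.

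**Assumed inputs.** The documents give no correlations, so I took a range:

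- rP, baseline PCL-5 with final PCL-5: 0.4 to 0.5
- rC, baseline CAPS-5 with final PCL-5: 0.3 to 0.5
- ρ, between the two baselines: 0.5 to 0.7

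Each person has one final-session score, so I treated the model as an analysis of covariance in completers.

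**Formulas.**

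- Residual variance with baseline PCL-5 only: 1 − rP².
- With both: 1 − R², where R² = (rP² + rC² − 2·rP·rC·ρ)/(1 − ρ²).
- Small-sample inflation of the standard error with k covariates at n = 32: f(k) = √[29/(29 − k)]. Going from one to two covariates multiplies the standard error by √(28/27) = 1.018.
- Net standard-error ratio = √[(1 − R²)/(1 − rP²)] × 1.018.
- Power: noncentral t with 30 − k degrees of freedom and noncentrality 1.02 × √(24 × 8/32) / [√(residual variance) × f(k)].

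Example with rP = 0.5, rC = 0.5, ρ = 0.5: R² = (0.25 + 0.25 − 0.25)/0.75 = 0.333. Residual variance goes from 0.750 to 0.667. The ratio is √(0.667/0.750) × 1.018 = 0.943 × 1.018 = 0.96.

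| rP | rC | ρ | Residual variance, without → with CAPS-5 | Net SE ratio | Power, without → with |
|---|---|---|---|---|---|
| 0.40 | 0.50 | 0.50 | 0.840 → 0.720 | 0.94 | 73.5% → 78.3% |
| 0.50 | 0.50 | 0.50 | 0.750 → 0.667 | 0.96 | 78.2% → 81.3% |
| 0.45 | 0.40 | 0.60 | 0.798 → 0.771 | 1.00 | 75.7% → 75.5% |
| 0.50 | 0.40 | 0.60 | 0.750 → 0.734 | 1.01 | 78.2% → 77.5% |
| 0.50 | 0.30 | 0.60 | 0.750 → 0.750 | 1.02 | 78.2% → 76.6% |

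I ran 45 combinations: rP and rC in steps of 0.05, ρ in steps of 0.1. The ratio runs from 0.94 to 1.02 with median 1.00, and is below 1 in 21 of the 45. Power changes by -1.6 to +4.8 points.

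**Simulation.** The formula takes no credit for the stratification, so I also simulated 20,000 trials per scenario at 24/8. Two strata were formed at the baseline CAPS-5 median, with 12 of 16 in each assigned to guided. This is a simplification, since the plan does not describe the urn.

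| rP, rC, ρ | SE ratio | Power, without → with | Type I error, without → with |
|---|---|---|---|
| 0.4, 0.5, 0.5 | 0.93 | 74.7% → 79.3% | 4.0% → 4.8% |
| 0.5, 0.5, 0.6 | 0.97 | 79.2% → 81.3% | 4.7% → 5.1% |
| 0.5, 0.4, 0.6 | 1.00 | 78.2% → 77.8% | 4.7% → 5.0% |
| 0.5, 0.3, 0.6 | 1.01 | 78.6% → 77.4% | 5.2% → 5.2% |

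The Monte Carlo standard error of a 5% rate is √(0.05 × 0.95/20,000), about 0.15 points, so 5.2% is compatible with 5%. Taking formula and simulation together, the standard-error ratio is about 0.93 to 1.02.

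**The case against.** Adjusting each outcome for its own baseline is standard. Baseline PCL-5 measures the same construct as baseline CAPS-5 and already absorbs much of what they share. Keeping the model small is reasonable with about 8 controls. The general covariate rule is also not empty: baseline CAPS-5 helps precision only if it predicts final PCL-5, and that is broadly when the rule would admit it.

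Most of this stands, and it rules out three stronger readings that a reader might take.

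- *That the plan excludes baseline CAPS-5 from the PCL-5 model.* It does not. The general rule can bring it in. The accurate statement is that it is not prespecified.
- *That the PCL-5 standard error is definitely too large, or its test invalid.* Neither is shown. The net effect is close to nil at mid-range and slightly adverse in several settings, and type I error is not inflated.
- *That the fix is worth a countable number of participants.* That comes from reading the gross fall in residual variance (0 to 14% over the grid) as a saving. Once the lost degree of freedom and small-sample inflation are counted, the median gain is nil. The 14% also requires the baseline interview to predict final self-report better than self-report's own baseline does (rC = 0.5 against rP = 0.4). With rC no larger than rP, the best case in the grid is a ratio of 0.96.

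The objection does not answer the prespecification point. A rule with no criterion, applied to observed outcomes, is not a substitute for naming the stratification variable in advance.

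**Conclusion.** The point holds as a minor, inexpensive improvement to the specification. Baseline CAPS-5 drives the allocation, is collected on everyone, and is a fixed covariate in one primary model but not the other. Its place in the PCL-5 model depends on an undefined outcome-based screen.

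The precision at stake is small: a standard-error ratio of about 0.93 to 1.02 and a power change of about -2 to +5 points at 24/8. The favourable end depends on baseline CAPS-5 carrying substantial information beyond baseline PCL-5. These figures rest on assumed correlations, 32 completers and roughly normal scores. The main benefit is that the covariates of a primary model would be fixed before outcomes are seen.

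**What to change.** In section 11.0, Hypothesis 2, state that both models include baseline CAPS-5 total score as a fixed continuous covariate because it is the stratification variable, and that the PCL-5 model also includes baseline PCL-5. Add that this holds regardless of the result of the association screen. If the sponsor prefers to leave it out of the PCL-5 model, the plan should say so and give the reason.

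The cost is one sentence, no new data and one degree of freedom. If baseline CAPS-5 adds nothing beyond baseline PCL-5, the standard error rises by at most about 2% and power falls by under 2 points over the range examined.
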